## 8.4. Abnormal Test Findings

The criteria for determining whether an abnormal objective test finding should be reported as an adverse event are as follows:

- Test result is associated with accompanying symptoms; and/or
- Test result requires additional diagnostic testing or medical/surgical intervention; and/or
- Test result leads to a change in trial dosing or discontinuation from the trial, significant additional concomitant drug treatment, or other therapy; and/or
- Test result is considered to be an adverse event by the investigator or sponsor.

Merely repeating an abnormal test, in the absence of any of the above conditions, does not constitute an adverse event. Any abnormal test result that is determined to be an error does not require reporting as an adverse event.

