**7.5. Analysis of Safety**

All safety analyses will be performed using the As-Treated population. No formal comparisons between the two treatment arms are planned. Safety and tolerability will be assessed by the incidence of treatment emergent-adverse events (TEAEs), changes in laboratory parameters and vital signs from baseline, and ECG.

An independent DMC will monitor safety during the study on a regular basis. The committee will operate independently from the Sponsor and the clinical investigators.

The primary responsibility of the DMC is to review the accumulating safety data on a regular and an ad hoc basis and make recommendations to the Sponsor regarding the continued conduct of the study. Safety data will be provided at regular intervals to the DMC in the form of summary reports or data listings from the Sponsor or its designated representative.

Details regarding DMC membership, schedule and format of meetings, format for presentation of data, access to interim data, method and timing of providing interim reports to the DMC, and

---

|           |   |                 |           |
|-----------|---|-----------------|-----------|
| Document: | C:\Users\q764206\AppData\Local\Microsoft\Windows\Temporary Internet Files\Content.Outlook\GWW33WM3\ATLAS_SAPFinal v8.0_06MAR2018.docx |                 |           |
| Author:   | [name] (Updated [name]; [name]; [name], [name])  | Version Number: | Final 8.0 |
|           |   | Version Date:   |           |

06MAR2018

Template No: CS\_TP\_BS016 – Revision 2  
 Effective Date: 01Feb2010

Reference: CS\_WI\_BS005

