**Statistical Analysis Plan**

- Subjects with a Grade 5 TEAE through 28 days of last dose of the study treatment
- Subjects with a Related Grade 5 TEAE at any time
- Subjects with a TEAE leading to dose modification (dose reduction or temporary interruption/discontinuation)
- Subjects with a TEAE leading to dose reduction
- Subjects with a TEAE leading to temporary dose interruption/discontinuation
- Subjects with TEAE leading to permanent discontinuation

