**7.5.1.2 Treatment Emergent Adverse Events of Special Interest**

The following TEAEs of special interests will be summarized for the as-treated population and by SOC and PT for each categorized treatment group. The list of MedDRA defined SOC and PTs for TEAEs of special interest are provided below and may be updated at the time of database lock based on the MedDRA version in use at the time of reporting and/or any additional safety information available from the Axitinib program that may determine a need to consider additional events of interest. Additionally, for the following special adverse events, Kaplan-Meier methods will be used to display the time to the first occurrence of each of these 13 event categories, if the number of events is  $\geq 10$  events per treatment arm:

| Adverse Events of Special Interest | Search Terms (MedDRA version 20.1)  |
|---|--|
| Cardiac disorders                         | Cardiac disorders – SOC
Cardiac and vascular investigations (excluding enzyme tests)- HLGT  |
| Nervous system disorders                  | Central nervous system vascular disorders- HLGT  |
| Vascular disorders                        | Embolism and thrombosis- HLGT
Pulmonary Embolism PT   |
| Renal vascular disorders                  | Renal vascular and ischaemic conditions (HLT)
Renal failure and impairment (HLT)
Renal hypertension and related conditions (HLT) |

Document: C:\Users\q764206\AppData\Local\Microsoft\Windows\Temporary Internet Files\Content.Outlook\GWW33WM3\ATLAS\_SAPFinal v8.0\_06MAR2018.docx  
 Author: [name] (Updated [name]; [name]; [name], [name]) Version Number: Final 8.0

Version Date: 06MAR2018

Template No: CS\_TP\_BS016 – Revision 2 Reference: CS\_WI\_BS005  
 Effective Date: 01Feb2010

Statistical Analysis Plan

|   |   |
|---|---|
| Haemorrhage                                 | Haemorrhage (excluding lab terms) SMQ (broad and narrow) and Haemorrhage laboratory terms SMQ (broad and narrow)  |
| Hypertension                                | Hypertension SMQ narrow   |
| Proteinuria                                 | MedDRA PTs: Albumin urine present, Proteinuria, Protein urine, and Protein urine present  |
| Thyroid Dysfunction                         | Thyroid dysfunction SMQ broad   |
| Venous Embolic and Thrombotic Events (VTE)  | Embolic and thrombotic events, venous SMQ narrow  |

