**7.5.4. Vital Signs, Physical Findings, and Other Observations Related to Safety**

Baseline for body weight and vital signs will be defined as the latest value recorded on or prior to dosing on Day 1. Summary statistics for actual values and change from baseline will be presented. Unscheduled body weight and vital signs measurements will be listed only.

The proportion of subjects meeting the following blood pressure criteria on 2 or more scheduled and unscheduled visits (need not be consecutive) after first dose (modified from JNC criteria to address single measurement per time point) (Chobanian et al., 2003) will be presented in a table:

- Normal: Systolic Blood Pressure (SBP)  $<120$  mmHg and Diastolic Blood Pressure (DBP)  $< 80$  mmHg
- Pre-hypertension\*: SBP 120-139 mmHg or DBP 80-89 mmHg
- Stage 1: SBP 140-159 mmHg or DBP 90-99 mmHg
- Stage 2: (SBP  $\geq 160$  mmHg and DBP  $<120$ ) or DBP 100-119 mmHg

\*Defined according to CTCAE v4.03 criteria.

The proportion of subjects with weight loss  $\geq 10\%$  after first dose will also be presented in a table.

ECOG PS and change from baseline in ECOG PS will be summarized using summary statistics, and will also be presented as a shift from baseline to post-baseline time points. Specifically, shift tables of ECOG score from baseline will be presented at each cycle as well as tables demonstrating from baseline to best and worst post baseline score. A mixed model will also be implemented to assess treatment differences in ECOG PS over time. Baseline ECOG will be

---

|           |   |                 |           |
|-----------|---|-----------------|-----------|
| Document: | C:\Users\q764206\AppData\Local\Microsoft\Windows\Temporary Internet Files\Content.Outlook\GWW33WM3\ATLAS_SAPFinal v8.0_06MAR2018.docx |                 |           |
| Author:   | [name] (Updated [name]; [name]; [name], [name])  | Version Number: | Final 8.0 |
|           |   | Version Date:   | 06MAR2018 |

Template No: CS\_TP\_BS016 – Revision 2  
 Effective Date: 01Feb2010

Reference: CS\_WI\_BS005

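### The Stage 2 blood-pressure row in SAP 7.5.4 excludes diastolic pressure of 120 mmHg or more, and no other row is defined for it

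*SAP*

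**What the plan says.** SAP section 7.5.4 lists four rows for measured blood pressure: Normal, Pre-hypertension, Stage 1 and Stage 2. A subject counts in a row if its criterion is met "on 2 or more scheduled and unscheduled visits (need not be consecutive) after first dose". Stage 2 is the highest row and has two limbs. The first is SBP of at least 160 mmHg joined by a logical AND to DBP below 120. The second reads "or DBP 100-119 mmHg". The list ends there.

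The SAP says the rows are adapted from published hypertension criteria. The only reason it gives for adapting them is that there is one measurement per time point.

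The same section handles blood pressure in two other ways. For scheduled visits, "Summary statistics for actual values and change from baseline will be presented". For the rest, "Unscheduled body weight and vital signs measurements will be listed only". Elsewhere, SAP 7.5.1.2 makes hypertension an adverse event of special interest, found by "Hypertension SMQ narrow". The overall adverse-event summary in SAP 7.5.1 includes "Subjects with a TEAE leading to temporary dose interruption/discontinuation". SAP 7.5 states that "No formal comparisons between the two treatment arms are planned".

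**The concern.** A severity table should not drop a reading from its top category because the reading was higher. Here both limbs of the top row carry an upper diastolic limit, and nothing sits above it. The stated reason for adapting the source criteria, one measurement per time point, does not explain why the highest diastolic values should be left out.

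Hypertension is a known effect of this drug. In the earlier Phase 3 trial summarised in Protocol section 1.1.4 (Table 1), it was reported in 40% of axitinib patients at any grade and 16% at Grade 3/4. This is the one table in the SAP that classifies measured pressure by subject. If axitinib raises pressure relative to placebo, any omission would tend to fall in the axitinib arm and make the Stage 2 row look better than the data. That direction is an inference; the documents give no frequency of DBP 120 or more in either arm.

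**Working it through.** The plan gives no figure to reproduce. The check is to code the four rows exactly as SAP 7.5.4 states them, apply them to readings, and repeat with the upper diastolic limit removed.

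Inputs, all from SAP 7.5.4, in mmHg:
- Normal: SBP < 120 and DBP < 80
- Pre-hypertension: SBP 120–139 or DBP 80–89
- Stage 1: SBP 140–159 or DBP 90–99
- Stage 2: (SBP ≥ 160 and DBP < 120) or DBP 100–119
- Counting: a row is met on at least 2 visits after first dose

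The SAP does not say whether a subject may appear in more than one row. Each row is counted separately here. The visit-level results do not depend on that choice.

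**Single visits, as written**

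| Reading | Rows met |
|---|---|
| 180/119 | Stage 2 |
| 180/120 | none |
| 200/130 | none |
| 150/119 | Stage 1 and Stage 2 |
| 150/120 | Stage 1 only |
| 130/120 | Pre-hypertension only |
| 220/110 | Stage 2 |

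The gap is diastolic only: 220/110 still counts as Stage 2. With DBP ≥ 120, a visit counts in no row if SBP ≥ 160. At lower SBP it can enter a lower row, but only through its systolic value.

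**All readings on a grid.** Take integer readings with DBP 120–139, SBP up to 239 and, as an assumed plausibility filter, pulse pressure of at least 20.
- Total: 100 + 99 + … + 81 = 20 × (100 + 81) / 2 = 1,810.
- SBP 160–239: 80 × 20 = 1,600, which meet no row.
- SBP 140–159: 20 + 19 + … + 1 = 210, which meet Stage 1 only.
- Meeting Stage 2: 0.

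The filter removes readings such as 130/120. A wider grid without it (SBP 70–260, DBP 40–160, DBP below SBP) gives the same picture: every pair that meets no row has DBP ≥ 120 and SBP ≥ 160.

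**With Stage 2 redefined as SBP ≥ 160 or DBP ≥ 100.** All 1,810 readings meet Stage 2, and their membership of the other three rows does not change. Of the 80 × 160 = 12,800 integer readings with DBP 40–119 and SBP 80–239, none changes. These are counts of possible readings, not of patients.

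**Subjects, under the two-visit rule**

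| Visits | As written | Redefined |
|---|---|---|
| 165/104, 180/118 | Stage 2 | Stage 2 |
| 165/104, 180/122 | no row | Stage 2 |
| 165/104, 150/119 | Stage 2 | Stage 2 |
| 165/104, 150/120 | no row | Stage 2 |
| 180/122, 184/124 | no row | Stage 2 |
| 155/121, 152/120 | Stage 1 | Stage 1 and Stage 2 |
| 165/104, 162/102, 180/122 | Stage 2 | Stage 2 |

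The first two pairs of lines isolate the fault: raising one diastolic value takes the subject out of Stage 2. The last line shows its limit: two other qualifying visits are enough to keep the subject in.

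**The case against.** The strongest reply is that this will rarely matter and that the information reaches the report by other routes. The protocol requires pressure of at most 140/90 at screening, does not start treatment if Day 1 readings are above that, and has patients monitor at home (sections 4.1, 6.2.1.1 and 5.3.4.2). Two site readings with DBP above 105 lead to interruption of dosing under section 5.3.4.2. Protocol 8.4 lists among its adverse-event criteria: "Test result leads to a change in trial dosing or discontinuation from the trial". Two readings of 120 or more in a subject on drug should therefore reach the adverse-event and dose-interruption summaries and, if coded as hypertension, the special-interest table. SAP 6.1.1 also reports maxima, so an extreme DBP at a summarised visit would be visible by arm.

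That stands as a limit on the consequence. It does not repair the count: an adverse-event table and a maximum do not say how many subjects met the top row. Readings at unscheduled visits are only listed, so they do not enter the maxima, although this table does count those visits.

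A second reply is that the table shells, named in the SAP contents, are not in the supplied text. A limit at exactly 120 is compatible with a further row there. That cannot be excluded, but the SAP text would still need to state it.

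A third is that the table is not exhaustive anyway: 165/104 with 150/95 gives one Stage 2 visit and one Stage 1 visit, and so no row. That is true, and the change below leaves it alone. It follows from requiring two visits, whereas the fault here is that a higher reading removes a subject.

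**Conclusion.** The rule is wrong as written. Under the SAP text no visit with DBP of 120 mmHg or more can count toward Stage 2, and with SBP of 160 or more it counts in no row. A subject with such a visit is missed from Stage 2 unless two other visits qualify. The visit-level result is certain from the text; the subject-level examples assume that rows are counted separately.

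The number of subjects affected is unknown and may be zero. The reach is one descriptive safety table: no endpoint or formal comparison uses it, and the adverse-event summaries, vital-sign summary statistics and listing of unscheduled measurements are unaffected. The conclusion concerns the SAP text and not the absent shells. The change should be made because the error is definite and the correction costs almost nothing.

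**What to change.** In SAP 7.5.4, define the Stage 2 row of this table as SBP ≥ 160 mmHg or DBP ≥ 100 mmHg, with no upper limit. If DBP ≥ 120 mmHg is of interest in itself, show it as a subset row beneath Stage 2, so that those subjects still count in Stage 2. Check that the table shell agrees. The counting of the other rows need not change.

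The cost is one line of SAP text and one line of code. It needs no new data and touches no dosing or blood-pressure management rule.

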**Statistical Analysis Plan**

---

included in the model as a covariate

Physical examinations will be listed only.

**7.5.5. Prior/Concomitant Medications**

Prior and concomitant medications will be coded using the WHO-drug (World Health Organization) coding dictionary.

Prior medications are defined as those medications stopped prior to the first day of study treatment. Concomitant medications are defined as those medications either stopped, ongoing or started on or after the first day of study treatment up to 28 days post the last day of study treatment.

Number and percentage of subjects taking all prior and concomitant medications will be summarized by ATC Class and WHO Drug Name.

A listing will be provided for prior and concomitant non-drug treatments and procedures.

Prior non-drug treatments and procedures are defined as those stopped prior to the first day of study treatment. Concomitant non-drug treatments and procedures are defined as those treatments and procedures that are either stopped, ongoing or started on or after the first day of study treatment.

Prior treatment for cancer under study (including drugs administered, start and stop date of each, and reason for taking the medication) will be provided in a listing.

Anti-tumor drug treatments taken at follow-up will also be listed and summarized using the WHO-drug coding dictionary. Start dates to be considered as occurring during follow-up will be those that are >28 days beyond the last day of study treatment.

## 9. Appendix A

**Table 1. Primary Endpoint Disease-Free Survival by Independent Review Committee Censoring Rules:**

|  |  | Date of event*/ censoring  | Censoring |
|--|--|---|------------------|
| No IRC confirmed recurrence or occurrence of secondary malignancy or death | Post baseline assessments performed  | Date of last IRC reviewed scan prior to receiving anti-tumor therapy, if applicable   | Yes              |
|  | No post baseline assessments performed   | Date of randomization   | Yes              |
| IRC confirmed recurrence, secondary malignancy or death                    | Baseline scan shows presence of disease  | Date of randomization   | No               |
|  | Further anti-tumor therapy received after randomization and before recurrence or occurrence of secondary malignancy or death (Subject does not have two or more consecutively missed/not readable IRC reviewed scans immediately prior to recurrence, secondary malignancy or death)** | Date of last IRC reviewed scan prior to receiving anti-tumor therapy  | Yes              |
|  | Further anti-tumor therapy received after randomization and before recurrence or occurrence of secondary malignancy or death and subject had two or more consecutively missed/not readable IRC reviewed scans immediately prior to recurrence, secondary malignancy or death)**        | Date of last IRC reviewed scan prior to the two consecutively missed/not readable scans and prior to receiving anti-tumor therapy** | Yes              |
|  | No anti-tumor therapy received after randomization (Subject does not have two or more consecutively missed/not readable IRC reviewed scans immediately prior to recurrence, secondary malignancy or  | Date of IRC confirmed recurrence or occurrence of secondary malignancy or death, whichever occurred first*                          | No               |

Document: C:\Users\q764206\AppData\Local\Microsoft\Windows\Temporary Internet Files\Content.Outlook\GWW33WM3\ATLAS\_SAPFinal v8.0\_06MAR2018.docx

Author: [name] (Updated [name]; [name]; [name], [name])

Version Number:

Final 8.0

Version Date:

06MAR2018

Template No: CS\_TP\_BS016 – Revision 2  
 Effective Date: 01Feb2010

Reference: CS\_WI\_BS005

Statistical Analysis Plan

|  |  |   |     |
|--|--|---|-----|
|  | death)**   |   |     |
|  | No anti-tumor therapy received after randomization but subject had two or more consecutively missed/not readable IRC reviewed scans immediately prior to recurrence, secondary malignancy or death** | Date of last IRC reviewed scan before two consecutively missed/not readable IRC reviewed scans ** | Yes |

\* Note: For subjects for whom there is site confirmation of recurrence or occurrence of secondary malignancy in the absence of IRC imaging confirmation, the date of IRC confirmation from histo-/cytopathology specimens will be selected as the date of event if available. For subjects for whom the IRC sees a finding on a scan that requires confirmation but an additional scan is not provided, if there is a subsequent pathology report available the pathology report could be the confirmation of the disease seen on the scan. In this case the scan date should be used as the date of recurrence or secondary malignancy.

\*\*Additional details regarding the definition of two or more consecutively missed or inadequate scans can be found in Appendix B. For subjects who died prior to missing two scheduled assessments, they will be coded as an event at the date of death and will not be censored as long as no anti-tumor therapy was given after randomization and before death.

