## 7.1.1. Primary Endpoint

DFS is defined as the time interval from the date of randomization to the first date of recurrence (distant or local recurrence of RCC) or the occurrence of a secondary malignancy or death. The primary DFS analysis will be based on assessments by the IRC. IRC will review all imaging data. Additionally, in cases for which there is site confirmation of recurrence or occurrence of a secondary malignancy in the absence of IRC imaging

confirmation, available local histo-/cytopathology reports will also be reviewed by the IRC oncologist to determine confirmation of recurrence or occurrence of a secondary malignancy.

Recurrence refers to relapse of the primary tumor in situ or at metastatic sites. The date of recurrence or the occurrence of a secondary malignancy is defined as the date of the tumor scan or the date of collection of the histo-/cytopathological specimen (for patients who have site confirmation of recurrence or occurrence of secondary malignancy in the absence of IRC imaging confirmation) that demonstrated unequivocal recurrence or a secondary malignancy according to protocol criteria. If both imaging and histo-/cytopatholigical confirmation of recurrence or sencondary malignancy are available, the earlier of the two dates will be considered.

For patients with no DFS event, DFS time will be censored at the date of the last scan prior to the time for the analyses. Patients alive who do not have post-baseline disease assessments will have their DFS times censored at randomization. For patients receiving further anti-tumor therapy prior to recurrence or occurrence of a secondary malignancy or death, DFS will be censored on the date of the last scan prior to taking the anti-tumor medication. Patients who miss 2 or more consecutive tumor scans immediately followed by an event will be censored at the date of the last objective tumor assessment prior to the missing/not readable scans.

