**Amendment#10** (Mar 2017): The primary endpoint was modified to include evaluations of available local histo-/cytopathology reports by an independent IRC oncologist for cases in which recurrence or occurrence of secondary malignancy had been confirmed by the site in the absence of IRC imaging confirmation. Specifically, the date of recurrence or the occurrence of secondary malignancy will be defined as the date of the tumor scan or the date of collection of the histo-cytopathological specimen (for subjects who have site confirmed recurrence or occurrence of secondary malignancy in the absence of IRC imaging confirmation) that demonstrated unequivocal recurrence or secondary malignancy according to protocol criteria. If both imaging and histo-/cytopathological confirmation of recurrence or secondary malignancy are available, the earlier of the two dates will be considered. In addition, the protocol was amended to include censoring subjects who have two or more consecutively missed or not readable scans immediately prior to an event. The date of censoring in these instances will be on the date of the most recent scan prior to the missing/not readable scans. The protocol was further amended to remove excluding as an event the occurrence of a second primary cancer that was basal cell carcinoma, squamous cell skin cancer or in situ carcinoma of the cervix uteri. Additionally, the protocol was also changed to record anti-tumor therapy even after 28 days after last treatment. More details were provided for analysis of DFS defined by assigning dates for events and censoring at scheduled scan dates.

---

|           |   |                 |           |
|-----------|---|-----------------|-----------|
| Document: | C:\Users\q764206\AppData\Local\Microsoft\Windows\Temporary Internet Files\Content.Outlook\GWW33WM3\ATLAS_SAPFinal v8.0_06MAR2018.docx |                 |           |
| Author:   | [name] (Updated [name]; [name]; [name], [name])  | Version Number: | Final 8.0 |
|           |   | Version Date:   | 06MAR2018 |

|                                       |                        |
|---------------------------------------|------------------------|
| Template No: CS_TP_BS016 – Revision 2 | Reference: CS_WI_BS005 |
| Effective Date: 01Feb2010             |                        |

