## 5. Efficacy Endpoints and Covariates

### 5.1. Primary Efficacy Endpoint

The primary endpoint is DFS, defined as the time interval (measured in years) from the date of randomization to the first date of recurrence (distant or local recurrence of RCC) or the occurrence of a secondary malignancy or death due to any cause. The primary DFS analysis will be based on assessment by the IRC. The IRC will review all available scans and in cases for which there is site confirmation of recurrence or occurrence of a secondary malignancy in the absence of IRC imaging confirmation, available local histo-/cytopathology reports will be reviewed by an independent IRC oncologist.

Recurrence refers to relapse of the primary tumor in situ or at metastatic sites. The date of recurrence or the occurrence of a secondary malignancy is defined as the earlier of:

- the date of the tumor scan or the date of collection of the histo-/cytopathological specimen (for subjects who have site confirmed recurrence or occurrence of a secondary malignancy in the absence of IRC imaging confirmation) that demonstrated unequivocal recurrence or a second malignancy according to protocol criteria

Per the IRC charter, radiological findings should be unequivocal. At the time of the final IRC review for a given data cut (interim or final), equivocal disease, identified by radiology requiring confirmation, is noted in the IRC data at the ‘Global Review’ with an indication of disease present and a date of recurrence/secondary malignancy recorded by the IRC as not applicable (N/A). As these findings require confirmation, they will not be counted as events in the DFS analysis unless, there is a subsequent pathology report which provides confirmation of the disease seen on the scan. In this case the scan date should be used as the date of recurrence or secondary malignancy.

In the absence of pathology to confirm the equivocal findings, these subjects will be censored at the date of last scan before anti-cancer therapy (if applicable). The last scan date includes the scan where the equivocal finding was noted.

For subjects identified as having the presence of disease at baseline by IRC review,

- Recurrence will be considered to have occurred on the date of randomization.

---

|           |   |                 |           |
|-----------|---|-----------------|-----------|

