**7. Statistical Analysis**

**7.1. Analysis of Primary Efficacy Endpoint**

**7.1.1. Disease-Free Survival Based on IRC Review**

Disease-Free Survival of the ITT Population based on the IRC review of tumor assessments will be summarized using the Kaplan-Meier method. Kaplan-Meier curves for each arm will be generated, and median DFS time will also be presented with corresponding 95% CI. The CI for the median will be calculated according to Brookmeyer and Crowley. To test the equality of DFS time in each arm a stratified log-rank test (using a stratification factor as defined in Section 5.4) will be used. Censoring rules as described in Table 1 of Appendix A will be implemented. The statistic of the test will be presented along with the associated two-sided p-value.

The estimated HR (Axitinib/Placebo) will be obtained using a Cox’s Proportional Hazards model with treatment group as well as a randomization stratification factor as a covariate. The stratification factor used in the analyses will be risk group as described in Section 5.4.1.

The significance level for the final DFS analysis will be 0.0442 as calculated using the O’Brien-Fleming method. (Assumes interim analysis at 184 events with a significance level of 0.0194).

Annual DFS rates up to 5 years for each treatment group will be estimated and presented with corresponding 95% CI. The CI for the survival function will be calculated using the complementary log-log transformation method.

The final analysis of the primary endpoint of DFS will be performed when approximately 245 DFS events based on IRC review are observed.

A subject listing for DFS will include, DFS time, censoring status, censoring reason, date of randomization and date of last tumor assessment. In addition, a listing of subjects with baseline disease as determined by the IRC, will be produced.

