Statistical Analysis Plan

---

and the targeted date for the 2nd-missed-date is 32 weeks after the last non-missing-date. After adding a 2-week window, the decision rule is: if the DFS event is >34 weeks after the last non-missing date, DFS time will be censored at the date of the last non-missing tumor scan prior to the DFS event, otherwise DFS time will be the non-censored time interval from randomization date to the date of DFS event.

- (2) The last-non-missing-date is before the 3-YR rand date, but the last-non-missing-date plus 16 weeks is beyond the 3-YR rand date.

In Scenario (2), the targeted date for the 1st-missed-date is 16 weeks after the last-non-missing-date, and the targeted date for the 2nd-missed-date is 16 weeks plus 26 weeks after the last-non-missing-date. After adding a 2-week window, the decision rule is: if the DFS event is >44 weeks) after the last-non-missing-date, DFS time will be censored at the date of the last non-missing tumor scan prior to the DFS event, otherwise DFS time will be the non-censored time interval from the randomization date to the date of DFS event.

- (3) The last-non-missing-date is beyond the 3-YR rand date.

---

Document: C:\Users\q764206\AppData\Local\Microsoft\Windows\Temporary Internet Files\Content.Outlook\GWW33WM3\ATLAS\_SAPFinal v8.0\_06MAR2018.docx  
 Author: [name] (Updated [name]; [name]; [name], [name])      Version Number: Final 8.0

Version Date: 06MAR2018

Template No: CS\_TP\_BS016 – Revision 2  
 Effective Date: 01Feb2010

Reference: CS\_WI\_BS005

Statistical Analysis Plan

---

Partial dates should be presented as --NOV1999 or - - - - - 1999 as needed.

Partial times should be presented as --:30 or 14:-- as needed.

Listings should be sorted according to the order of the columns.

---

|           |   |                 |           |
|-----------|---|-----------------|-----------|
| Document: | C:\Users\q764206\AppData\Local\Microsoft\Windows\Temporary Internet Files\Content.Outlook\GWW33WM3\ATLAS_SAPFinal v8.0_06MAR2018.docx |                 |           |
| Author:   | [name] (Updated [name]; [name]; [name], [name])  | Version Number: | Final 8.0 |
|           |   | Version Date:   | 06MAR2018 |

Template No: CS\_TP\_BS016 – Revision 2  
Effective Date: 01Feb2010

Reference: CS\_WI\_BS005

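### The notes to SAP Appendix A Tables 1, 4 and 5 date pathology-only DFS events at IRC confirmation, but SAP 5.1 and the protocol date them at specimen collection

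*SAP*

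**What the plan says.** The primary endpoint is DFS by IRC assessment. Since Amendment 10 (March 2017) it also counts cases that the site has confirmed and IRC imaging has not. SAP 3.4.2 describes the change: "The primary endpoint was modified to include evaluations of available local histo-/cytopathology reports by an independent IRC oncologist".

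SAP 5.1 takes as the event date the earlier of "the date of the tumor scan or the date of collection of the histo-/cytopathological specimen". Protocol 7.1.1 and the protocol summary use the same pair of dates and take the earlier when both are available. For pathology, the protocol date is "the date of collection of the histo-/cytopathological specimen".

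SAP 7.1.1 then says of the primary analysis: "Censoring rules as described in Table 1 of Appendix A will be implemented". The asterisked note under that table covers site-confirmed cases without IRC imaging confirmation and says "the date of IRC confirmation from histo-/cytopathology specimens will be selected as the date of event if available". The notes under Table 4 (no censoring for therapy or missed scans) and Table 5 (new therapy as an event) repeat it.

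Two other Table 1 rules depend on when the event is taken to have occurred. One censors a patient with "Further anti-tumor therapy received after randomization and before recurrence or occurrence of secondary malignancy or death". The other censors for two missed scans; Appendix B applies it in the first three years "if the DFS event is >34 weeks after the last non-missing date", with a 44-week limit around the three-year mark.

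**The concern.** The day tissue is taken and the day an independent oncologist confirms disease from the report are different days, and the second cannot precede the first. Two programmers could each follow the SAP and derive different DFS times for the same patient, in the primary analysis and in two sensitivity analyses.

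The affected cases are the ones Amendment 10 brought into the endpoint. At stake are their event times and, if the late date is used throughout Table 1, whether some of them count as events. Censoring a patient whose recurrence has been proven would be potentially informative. Table 4 drops both censoring rules but keeps the same note, so it would retain the event with the late date.

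**Working it through.** **1. The passages side by side**

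| Place | Date for a site-confirmed event without IRC imaging confirmation |
|---|---|
| Protocol summary and 7.1.1 | Scan or specimen collection |
| SAP 5.1 | Scan or specimen collection, whichever is earlier |
| SAP 3.4.2 on Amendment 10 | "the date of the tumor scan or the date of collection of the histo-cytopathological specimen" |
| SAP Appendix A, notes to Tables 1, 4 and 5 | IRC confirmation |

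SAP 3.4.2 is a change history and only corroborates; the conflict stands on SAP 5.1 and protocol 7.1.1 alone. Protocol 9.2.1 points the same way: its scheduled-scan sensitivity analysis replaces the actual scan date or the specimen collection date.

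**2. Which text governs.** SAP Section 1 says the SAP supersedes the protocol, but that major changes to the primary endpoint or its analysis will appear in a protocol amendment. Protocol version 10, on which this SAP is based, uses the collection date. Nothing in either document announces a move to the confirmation date.

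**3. Post-dating.** Let R be randomization, C specimen collection and V IRC confirmation, with no earlier qualifying scan. By the formula in SAP 5.1:

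- collection date: DFS = (C − R + 1)/365.25
- literal note: DFS = (V − R + 1)/365.25
- difference: (V − C)/365.25 years, or 7L/365.25 for a lag of L weeks.

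The documents give no lag, so these values of L are assumptions:

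| L (weeks) | Added DFS (years) |
|---|---|
| 4 | 0.08 |
| 12 | 0.23 |
| 26 | 0.50 |
| 52 | 1.00 |
| 104 | 1.99 |

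The oncologist review entered in March 2017. A specimen taken a year before that would therefore carry a literal lag of at least about 52 weeks.

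**4. Missed-scan rule, if applied to the late date.** The limits in Appendix B reproduce: 16 + 16 + 2 = 34 weeks (scenario 1) and 16 + 26 + 2 = 44 weeks (scenario 2). Let the specimen be taken g weeks after the last evaluable scan, with no evaluable scan afterwards. An event kept under the collection date becomes censored when g + L exceeds the limit:

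| g (weeks) | 34-week limit: censored if L exceeds | 44-week limit: censored if L exceeds |
|---|---|---|
| 16 | 34 − 16 = 18 | 44 − 16 = 28 |
| 24 | 34 − 24 = 10 | 44 − 24 = 20 |

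An evaluable scan between collection and confirmation restarts the count from that scan.

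**5. Therapy rule, if applied to the late date.** Suppose anti-tumor therapy starts at T, after C but before V. Measured against C, therapy follows the event and the patient stays in the uncensored row of Table 1. Measured against V, therapy precedes the event and the patient is censored at the last IRC-reviewed scan before T. In Table 5 the same patient would have an event at T, provided the missed-scan rule did not apply. Protocol 5.5.2 and 6.5.1 encourage investigators to await the IRC but do not require it, so therapy in the gap is possible.

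**6. Design figures.** SAP 7.1.1 places the final analysis at approximately 245 IRC events. Events not counted would have to be replaced by later ones, so the analysis would mainly be delayed. The 245 events and the nominal levels 0.0194 and 0.0442 do not change under either dating rule.

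**The case against.** The strongest reply is that the note is loosely worded and changes no rule. Elsewhere in Table 1, the date of an IRC-confirmed recurrence presumably means the scan date and not the day of the reading. The phrase about specimens may likewise mean the date belonging to the specimen. The protocol and SAP 5.1 support that intent, so a reader who infers that the SAP deliberately redefined the endpoint goes too far. The contradiction still stands: the same note says scan date where it means the scan date, and it never mentions collection.

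A reader might also infer that most or nearly all pathology-only events would be censored. The documents do not support this, for three reasons.

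- The therapy row of Table 1 asks whether therapy came before recurrence. It does not refer to the note's date, and SAP 5.1 dates recurrence by scan or collection. A patient biopsied and then treated is censored only if the programmer carries the late date into that row.
- Protocol 5.5.2 and 7.1 require tumor assessments to continue after an investigator's finding until the IRC determines recurrence or secondary malignancy. Those scans narrow the missed-scan route.
- No document says how often therapy starts in the gap.

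Finally, a reader might infer a loss of power. That would apply to an analysis at a fixed cutoff; this one is triggered by events.

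**Conclusion.** The inconsistency is real, is in current text and concerns the primary endpoint. On the literal reading, each affected event is post-dated by exactly the review lag. Censoring is a further possibility that needs two things: the late date must be carried into the other rules, and either therapy must start in the gap or the 34- or 44-week limit must be passed with no later evaluable scan.

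Only site-confirmed cases without IRC imaging confirmation are affected. Their number, the review lag and any difference between arms are not given, so neither the size nor the direction of an effect on the hazard ratio can be stated. No bias in a particular direction and no power loss is claimed. The case for correction is that the date and status of a primary-endpoint event should not depend on which part of the SAP a programmer follows.

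**What to change.** In the notes to Appendix A Tables 1, 4 and 5, replace the IRC confirmation date with: *date of collection of the specimen on which the IRC oncologist confirmed recurrence or secondary malignancy*.

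In the same edit:

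- keep the rule that the earlier of scan and specimen date applies when both confirm disease;
- keep the second half of the note, which dates an equivocal scan finding later confirmed by pathology at the scan and already agrees with SAP 5.1;
- state that the anti-tumor-therapy and missed-scan rules, where used (Tables 1 and 5), are applied to the resulting date.

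The cost is a sentence or two in three table notes. No protocol amendment is needed, because the change brings the SAP back to the protocol, and no design figure moves. It should be settled before unblinding. Any DFS dataset already programmed to the literal note would need its event dates and censoring flags re-derived.
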